	This feasibility study is a prospective, randomized, two-period crossover multi-center study of 2 weeks of home use of Control-IQ 1.5 technology (run-in period), followed by 2 weeks of home use of Control-IQ 2.0 technology at one target, followed by 2 weeks of home use of Control-IQ 2.0 at another target. This automated insulin dosing (AID) system will be evaluated in multiple age groups, with late bolus meal challenges.						
	t:slim X2 insulin pump with Control-IQ technology 1.5 (Run-In Period) t:slim X2 insulin pump with Control-IQ technology 2.0 (Treatment Periods)						
-	The objectives of the study are to assess safety of and explore glycemic outcomes with Control-IQ technology 2.0 in adults, children and preschoolers with type 1 diabetes using different targets and after late bolus meal challenges.						
Number of Sites	Up to 6 clinical sites in the US.						
Study Design	Randomized sequence, prospective safety study						
	Up to 100 participants signing consent to use the study devices, so that at least 72 complete the study (at least 30 participants age 14+, at least 30 participants age 6-13, and at least 12 participants age 2-5), plus local contacts for adult participants. Enrollment goal is at least 50% of all participants in each age group have an HbA1c at baseline of \geq 7.5%.						

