	 Age 2 to ≤ 81 years Diagnosis of type 1 diabetes for at least 1 year, or at least 6 months for age 2-5 years at enrollment Prior Dexcom CGM user, with at least 11 of the prior 14 days of CGM use available for download at the screening visit to confirm eligibility Total Daily Insulin Dose (TDD) at least 2 units/day Weight ≥ 20 lbs HbA1c ≤ 10.5% For participants <18 years old, living with one or more parent/legal guardian knowledgeable about emergency procedures for severe hypoglycemia, present with the participant during and for 5 hours (3 hours for participants age 2-5) after the meal challenges, and willing to use the Dexcom Follow app (with push notifications turned on) for the duration of the study. For participants ≥18 years old, availability of a local contact who has access to the study participant, knows their whereabouts, can be available to assist during the late bolus meal challenges, agrees to be promptly available if contacted by study staff, and willing to use the Dexcom Follow app (with push notifications turned on) for the duration of the study. If the participant lives alone, the local contact must live within 30 minutes and have access to the subject overnight. Investigator has confidence that the participant and/or parent/guardian can successfully operate all study devices and is capable of adhering to the protocol. Willing to use only aspart (novolog) or lispro (humalog) insulin with the study devices, with no use of long-acting basal insulin injections, or inhaled insulin with the study devices. Have current glucagon product to treat severe hypoglycemia (injectable or nasal) 						

12. Willing and able to perform the study late bolus meal challenges.

Eligibility to enroll in the study will be assessed based on the following exclusion criteria:

- 1. More than 1 episode of diabetic ketoacidosis (DKA) in the past 6 months
- More than 1 episode of severe hypoglycemia (needing assistance) in the past 6 months
- 3. Inpatient psychiatric treatment in the past 6 months
- 4. For Female: Currently pregnant or planning to become pregnant during the time period of study participation
 - a. A negative pregnancy test will be required for all females of childbearing potential
 - b. Counseling on appropriate birth control options will be provided to all females of child-bearing potential

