- Concurrent use of any non-insulin glucose-lowering agent, other than metformin (for example, GLP-1 agonists, Symlin, DPP-4 inhibitors, SGLT-2 inhibitors, sulfonylureas).
- 6. Hemophilia or any other bleeding disorder
- 7. Hemoglobinopathy
- 8. History of heart, liver, lung or kidney disease determined by investigator to interfere with the study
- 9. History of allergic reaction to Humalog or Novolog
- 10. Use of any medications determined by investigator to interfere with study
- 11. Significant chronic kidney disease (which could impact CGM accuracy in investigator's judgment) or hemodialysis
- 12. Concurrent use of any medication that could interfere with the study CGM, such as hydroxyurea
- 13. History of adrenal insufficiency
- 14. History of abnormal TSH consistent with hypothyroidism or hyperthyroidism that is not appropriately treated
- 15. History of gastroparesis
- A condition, which in the opinion of the investigator or designee, would put the participant or study at risk
- 17. Participation in another pharmaceutical or device trial at the time of enrollment or anticipated for during the time period of study participation
- 18. Employed by, or having immediate family members employed by Tandem Diabetes Care, Inc., or having a direct supervisor at place of employment who is also directly involved in conducting the clinical trial (as a study investigator, coordinator, etc.); or having a first-degree relative who is directly involved in conducting the clinical trial

Participant Duration

Approximately 6-12 weeks

Study Endpoints

The adult, pediatric and preschool populations will be combined for the analysis of primary and secondary endpoints. Separate analyses also will be performed for the adult, pediatric and preschool cohorts for the primary and secondary endpoints. CGM data collected during the challenge periods will not contribute to overall analysis of CGM metrics. The three study time periods are the Run-In period with Control-IQ technology 1.5, treatment period with Control-IQ technology 2.0 at the standard target, and treatment period with Control-IQ technology 2.0 at the lower target, where the order of treatment periods will be randomized.

Primary Endpoints:

- Severe hypoglycemia (with cognitive impairment such that assistance of another individual is needed for treatment) during study compared with data on severe hypoglycemic events reported by T1D Exchange clinic registry over a 3-month time period

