8.3 Sample Size

comparing continuous outcomes.

The sample size of at least 30 adults and adolescents age 14+ years old, 30 children age 6-13 years old, and 12 preschool participants age 2-5 years of age who will complete the trial was selected to have a reasonable time period of use in each age cohort to establish safety, with each subject completing 2 weeks of Control-IQ 1.5 technology use, 2 weeks of Control-IQ 2.0 technology use with the target of 112.5 to 160 mg/dL, and 2 weeks of Control-IQ 2.0 technology use with the target of 90-130 mg/dL. The choice of sample size is not based on statistical principles. In addition, the sample size assures a reasonable number of late bolus meal challenges completed.

There is a further enrollment goal of at least half of all participants in each age group have an HbA1c at baseline of $\geq 7.5\%$, and have at least 6 participants age 14-17.

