Safety events (not including CGM defined events defined in sections 6.2.2, 6.2.3, and 6.2.4) will be based on Safety analysis set, and tabulated for each primary endpoint as the number of events per participant, the number of participants with ≥ 1 event, and the rate of events per 100 person-years. A 95% confidence interval will be calculated for the rate of events per 100 person-years.

Since study eligibility excluded participants with 2 or more severe hypoglycemia or DKA events in the

Since study eligibility excluded participants with 2 or more severe hypoglycemia or DKA events in the prior 6 months, an unbiased comparison of the event rate during the Treatment Period with the pre-study event rate is not possible. Therefore, the severe hypoglycemia and DKA event rates will be compared with the T1D Exchange data, which reported the frequency of 1 or more severe hypoglycemia and DKA events in the prior 3 months. The proportion of participants with events during the Treatment Period (each

958

959

960

961

period separately) will be compared with the run-in period as well as with the T1D Exchange frequency.
Differences in proportions across the three study periods (two active treatments and the run in) will be estimated in a pairwise fashion, and statistical significance will be assessed using a normal approximation to a binomial distribution.

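### The T1D Exchange benchmark for severe hypoglycemia and DKA is not defined by age or standardised to the trial's quota-driven age mix, so the combined comparison may be confounded by age and the cohort comparisons have no stated matched benchmark

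*Combined protocol and SAP*

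**What the plan says.** **Comparator.** Section 8.6.1 explains that eligibility rules out an unbiased comparison with participants' own pre-study event rates, and turns to the registry's frequency of one or more events in the prior 3 months. The proportion with an event, for each treatment period separately, "will be compared with the run-in period as well as with the T1D Exchange frequency". Section 8.2 refers only to historical published data. The reference list cites a 2016-2018 registry report but reproduces none of its figures. The synopsis names the registry for both SH and DKA; section 8.4 names it only for SH.

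**Population.** The synopsis (Study Endpoints) states: "The adult, pediatric and preschool populations will be combined for the analysis of primary and secondary endpoints". It then adds separate analyses of the same endpoints for the adult, pediatric and preschool cohorts.

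**Age mix.** The synopsis sets the size as "Up to 100 participants signing consent to use the study devices, so that at least 72 complete the study", with "at least 30 participants age 14+, at least 30 participants age 6-13, and at least 12 participants age 2-5". Section 8.3 adds: "The choice of sample size is not based on statistical principles". Eligible ages are "Age 2 to ≤ 81 years", and section 8.3 also aims to "have at least 6 participants age 14-17", so the oldest cohort mixes adolescents and adults.

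**Not stated anywhere.** The documents give no registry frequency, overall or by age. They assign no benchmark to a cohort and describe no weighting to the trial's age mix.

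**The concern.** The registry is the external comparator for the first two primary endpoints. A registry figure carries the age mix of the registry, whereas this trial's age mix follows enrolment quotas that put 58% of the minimum number of completers under 14. If SH or DKA frequency depends on age, a crude registry figure is not what these participants would be expected to show even if the device had no effect.

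The issue is sharper for the cohort analyses, where a preschool result could be set against a figure drawn mainly from older people. Section 1.1.2 indicates that the younger cohorts have the least prior evidence: the marketed system is approved from age 6, and the earlier Control-IQ 2.0 study enrolled ages 14 and over.

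The plan chose the registry because its first-choice comparison would have been biased, so comparability matters on its own reasoning. Leaving the age bands open also allows the benchmark to be chosen after the events are known.

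**Working it through.** **1. The plan's own figure.** 30 + 30 + 12 = 72, as stated. Shares at the minima: 30/72 = 41.7% aged 14+, 30/72 = 41.7% aged 6-13, 12/72 = 16.7% aged 2-5.

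**2. The mix is not fixed.** The quotas are minima for completers, with up to 100 consenting. The Safety analysis set (section 8.5) is everyone who initiates the Treatment Period and uses the device. If all 100 did so, the 14+ share could run from 30% to 100 − 30 − 12 = 58%, and the 2-5 share from 12% to 100 − 60 = 40%.

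**3. Formula.** Let *r* be the frequency under 14 divided by the frequency at 14+, *s* the registry share aged 14+, and *w* the trial share aged 14+. For simplicity, one frequency is used for both under-14 cohorts.

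Standardised ÷ pooled benchmark = [*w* + (1 − *w*)*r*] / [*s* + (1 − *s*)*r*]

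The documents give neither *r* nor *s*. Assumed ranges: *r* from 0.33 to 3, *s* from 0.6 to 0.9. With *w* = 30/72:

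| *r* | *s* = 0.6 | *s* = 0.7 | *s* = 0.8 | *s* = 0.9 |
|---|---|---|---|---|
| 0.33 | 0.83 | 0.76 | 0.70 | 0.65 |
| 0.5 | 0.89 | 0.83 | 0.79 | 0.75 |
| 1 | 1.00 | 1.00 | 1.00 | 1.00 |
| 2 | 1.13 | 1.22 | 1.32 | 1.44 |
| 3 | 1.20 | 1.35 | 1.55 | 1.81 |

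Example: *r* = 2, *s* = 0.8 gives (0.417 + 1.167)/(0.8 + 0.4) = 1.583/1.2 = 1.32. The ratio is 1.00 if *r* = 1, and also for any *r* if *s* = *w*.

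**4. Dependence on the final mix.** At *r* = 2 and *s* = 0.8, *w* = 0.30 gives 1.70/1.2 = 1.42, and *w* = 0.58 gives 1.42/1.2 = 1.18.

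**5. Cohorts.** A cohort's own frequency ÷ pooled benchmark is *r*/[*s* + (1 − *s*)*r*] under 14 and 1/[*s* + (1 − *s*)*r*] at 14+. For *s* = 0.6 to 0.9:
- *r* = 0.5: 0.53 to 0.63 under 14; 1.05 to 1.25 at 14+.
- *r* = 2: 1.43 to 1.82 under 14; 0.71 to 0.91 at 14+.

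**6. In participants.** Assume a pooled 3-month frequency of 6% and *s* = 0.8. The pooled figure implies 72 × 0.06 = 4.3 participants with an event.
- *r* = 0.5: the 14+ frequency is 0.06/0.9 = 6.67%; the standardised benchmark is 6.67% × 0.708 = 4.7%, or 3.4 participants.
- *r* = 2: the 14+ frequency is 0.06/1.2 = 5.0%; the standardised benchmark is 5.0% × 1.583 = 7.9%, or 5.7 participants.

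Scaled to one 2-week period by 1 − (1 − *p*)^(14/91.3), assuming a constant rate, these become 0.7 (pooled), 0.5 and 0.9.

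**7. Window and precision.** The window ratio is 91.3/14 = 6.5, larger than any age ratio in the assumed range. With zero events, the exact two-sided 95% upper limit 1 − 0.025^(1/*n*) is 5.0% for *n* = 72, 11.6% for *n* = 30 and 26.5% for *n* = 12.

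**The case against.** The strongest reply is that this is an unspecified detail of an exploratory comparison. Section 8.2 declares no formal hypotheses and rules out formal inference from the p-values. No decision depends on the registry figure: suspension in 6.6.2 rests on event counts, and opening the 2-5 cohort in 2.1 rests on device effects, the stopping criteria and a safety review. Section 8.6.1 also compares with the run-in, where the same participants serve as their own control and age mix cannot confound. Fewer than one participant with an event per 2-week period is expected in the illustration, with or without standardisation. All of this stands, and it limits the importance of the point.

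A reader might also infer three stronger things, none of which the documents support:

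- **That the plan commits to one all-ages figure for every cohort.** The wording is singular, and a crude figure is the default reading for the combined comparison. But no value is given, and age-specific values are not excluded.
- **That the comparison is confounded by age.** This requires both a registry frequency that varies with age and a registry age mix unlike the trial's. Neither is in the documents, and the assumed ranges give ratios on both sides of 1.
- **That the age mix is fixed at 30:30:12.** The quotas are minima. At the 58% limit, a registry with the same 14+ share would give a ratio of 1.00 whatever the age gradient across 14.

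The reply does not remove the gap. The comparison will be calculated and reported, by cohort as well as combined, against a benchmark whose age composition nobody has defined. Fixing the window alone would leave that unchanged.

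**Conclusion.** The point holds as a conditional one. The benchmark for SH and DKA is not defined by age and not standardised to the trial's age mix, and the cohort comparisons have no stated matched value. Whether this biases the combined comparison, in which direction and by how much, cannot be determined from the documents.

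The illustrative range of 0.65 to 1.81 for the combined benchmark rests entirely on the assumed age gradient and registry age share, on the 30/30/12 minima, and on one frequency for all under-14s. Because the comparison is exploratory, events are few and the window mismatch is larger, this is a worthwhile inexpensive improvement and not a threat to the trial's conclusions.

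**What to change.** Add one paragraph to section 8.6.1, settled before analysis:

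1. State the registry frequencies for SH and DKA and the age bands they come from.
2. For the combined population, compute the expected number of participants with an event by applying the age-band frequencies to the actual Safety analysis set numbers in each age group (indirect standardisation). Report observed versus expected with an exact interval. Where registry bands cut across the 14+ cohort, count participants by registry band.
3. For each cohort, use the matching band. If none exists, which may be so for ages 2-5, report that cohort without a registry comparison.
4. Align the registry's 3-month window with the 2-week periods and state the assumption used, such as a constant event rate. Without this, observed versus expected cannot be interpreted.

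**Cost.** No change to design, enrolment or data collection. Age-band frequencies are less precise than a pooled figure, and their availability from the cited registry report is an assumption. The cohort intervals will remain wide, so the gain is a benchmark that is defined in advance and less open to age bias, not greater precision.

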8.6.2 Analysis of Other Safety Endpoints

966

976

990

995

1003 1004

Safety summaries will be based on Safety analysis set. All adverse events reported over the course of the study will be summarized by study period for run-in and both treatment periods separately and overall. Adverse events will be tabulated by System Organ Class and Preferred Term based on MedDRA version 22.0. Adverse events will also be summarized by seriousness, severity, and relationship to study procedures and the investigational device. Except where indicated, a subject reporting the same adverse event more than once will be counted once when calculating the number and percent of subjects with that particular event.

Adverse events leading to death or to discontinuation from the study will be listed separately. A listing of all adverse events will be provided.

8.6.3 Analysis of CGM Endpoints

CGM metrics will be assessed in CGM analysis set, and computed for the Run-In and both Treatment Periods separately. CGM metrics will be computed per subject over 24 hours, during daytime (6am-11:59pm), and during nighttime (12am-5:59am), as well as by age cohort (adults/adolescents, children 6 – 13, and preschool), baseline HbA1c cohort (HbA1c at baseline of ≥ 7.5%,yes/no), and target activity use as specified by the device (standard target, lower target, sleep activity, and exercise activity). The main statistical comparison will be made between the three 2-week periods (Run In, Treatment

The main statistical comparison will be made between the three 2-week periods (Run In, Treatment Period at standard target, Treatment Period at lower target). The comparison will be pairwise – Run-in vs standard targe, Ru-in vs lower target, and standard vs lower target. The percent time in glycemic ranges will be calculated as the number of measurements in the specified range divided by the total number of measurements for which it can be determined whether or not the measurement was in specified range.

The "Low" and "High" CGM readings will be included in all analyses. Percent time will be compared using a paired t-test assuming sufficient normality assumptions hold, otherwise an appropriate non-parametric method will be utilized.

8.6.4 Analysis of Late Bolus Meal Challenges

All analyses in section 8.6.4 will be conducted in the late bolus meal challenge analysis set. Data included in these analyses will be restricted to data during the meal challenge window (start of meal through 5 hours from meal imitation [3 hours for age 2-5]). The subgroups assessed will be the same as sections 8.6.1 − 8.6.3 (age cohort, baseline HbA1c cohort (HbA1c at baseline of ≥ 7.5%. yes/no), etc.)

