1.3.1.3 Hypoglycemia

- As with any person having type 1 diabetes and using insulin, there is always a risk of having 59
- hypoglycemia. The frequency of hypoglycemia should be no more and possibly less than it would be 60
- as part of daily living. Symptoms of hypoglycemia can include sweating, jitteriness, and not feeling well. 61
- There is the possibility of fainting or seizures (convulsions) and that for a few days the participant may 62
- not be as aware of symptoms of hypoglycemia. A CGM functioning poorly and significantly over-63
- reading glucose values could lead to inappropriate insulin delivery. The study meal challenges, requiring 64
- boluses to be delivered late, could increase the risk of hypoglycemia. 65

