3.1.3 Training on Management of Hyperglycemia

- The t:slim X2 with Control-IQ system will issue a predictive hyperglycemia alert (Control-IQ High Alert)
- when the system has increased insulin delivery, but detects a CGM value above 200 mg/dL and does not
- predict the value will decrease in the next 30 minutes. During the course of the study, participants will be
- permitted to change the CGM high glucose threshold alert setting on their device or mobile app, but will
- be instructed to choose a value no greater than 300 mg/dL.
- If the participant receives a Control-IQ High Alert, a prompt appears on the user interface to check the
- site for occlusion and test blood glucose.
- 320 If a participant's CGM reading is >300 mg/dL for more than 60 minutes or is ≥400 mg/dL at any point,
- the participant will be instructed to take the following steps:
- Perform a blood glucose meter check.
- If the blood glucose is >300 mg/dL, check for blood ketones with the study ketone meter.

- If the ketone level is ≥ 0.6 mmol/L (or ≥ 2.5 mmol\L at any time), take correction insulin, change insulin (pump) infusion site and contact study staff. Continue to monitor their glucose and blood ketone levels until they return to normoglycemia and ketones are < 0.6 mmol/l.
 - ◆ If ketones are <0.6 mmol/l, participants will be advised to continue to monitor their glucose until it returns to normoglycemia and to repeat the ketone measurement in 90 minutes if necessary
- If correction insulin is administered via insulin syringe, turn Control-IQ off for four hours and until glucose level has returned to <180 mg/dL.

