491 492 493	A paper logbook will be provided to participants that includes a page to record details about each challenge and procedural instructions about how participants will conduct these challenges. This material will be reviewed with each participant, and will be used for source verification for the eCRF database.
494 495 496 497 498	Before starting each challenge, participants (or parent/guardian if the participant is < 18 years of age) must assure the participant has a working CGM and Control-IQ is active. For pediatric participants, the participant's parent or guardian must remain with the child at all times and monitor CGM readings frequently during and through meal completion plus 5 hours (3 hours for participants age 2-5). Snacks and glucagon must be available for use during and after each challenge.
499 500 501 502	Participants will be instructed to communicate with study staff within one day prior to each challenge to review procedures and to have a contact with study staff no more than 1 day after the completion of each challenge. The participant or parent/guardian must have an on-call phone number for the study team prior to initiation of each challenge.
503 504	Hyperglycemia and Hypoglycemia treatment guidelines (sections 3.1.3 and 3.1.2) remain in effect for the challenges, and will be reviewed with participants prior to each challenge.
505 506	Site staff will directly contact the participant if they do not receive a follow up contact from participants when 24 hours have passed since the time of completion of the planned challenge.
507	5.1.1 Late Bolus Meal Challenges
508 509	All challenges will be performed with the last meal of the day (dinner) and participants will be instructed not to snack after dinner on days they are performing meal challenges, unless it is to treat hypoglycemia.
510 511 512	Participants will also be instructed not to use sleep activity for at least 5 hours (3 hours for participants age 2-5) once starting the meal challenge. Participants will be reminded to disable sleep activity if it is inadvertently activated during the challenge, and to re-enable it at the end of the challenge.
513	Time zero (start of the challenge) is at the first bite of food for the study meal.
514 515	During each two week treatment period with Control-IQ technology 2.0 use, the two meal challenges will consist of:

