516 517 518	 Full bolus for the given carbohydrates and calculated correction, given 45 minutes after starting the meal, based on calculated bolus dose using the bolus calculator (with full amount of carbohydrates entered).
519 520 521	• Full bolus for the given carbohydrates and calculated correction, given 45 minutes after starting the meal, based on calculated bolus dose using the bolus calculator (with full amount of carbohydrates entered) AND enabling the late bolus feature to 45 minutes later.
522	For each meal challenge, participants will:
523 524	1. Be in a fasting state for two hours prior to consuming the last meal of the day, with the last manual insulin bolus more than two hours prior to the meal.

- 525 2. For participants age 6+, only begin the meal challenge if CGM glucose is between 70 mg/dL and 200 mg/dL, and CGM trend arrow is not down.
- For participants age 2-5, only begin the meal challenge if CGM glucose is between 70 mg/dL and 250 mg/dL, and CGM trend arrow is not down.
- 529 Subjects with hyperglycemia > 200mg/dL will reschedule their challenge for another time. If < 530 To mg/dL, carbohydrate treatment can be given, after which the meal challenge can continue.
 - 3. Pediatric participants age 2-5 should have a meal with at least 20 grams of carbohydrates. Participants age 6-13 should have a meal with at least 35 grams of carbohydrates. All other participants should have at least 50 grams of carbohydrates for the study meal challenges. *Each participant should use the same meal for all of their meal challenges in the study. Participants will be encouraged to use the same frozen entrée of their choice for consistency.*
 - 4. Do their best to complete the meal within 30 minutes of starting to eat.
 - 5. Write down the start and end time of eating the meal, as well as the meal content (to include amount of carbohydrate, protein and fat) on the study provided logbook.
 - 6. Bolus for the meal 45 minutes after starting to eat, entering the full carbohydrate amount and using the recommended dose from the bolus calculator. For one of the two challenges during a single treatment period, use the bolus calculator but do not change the bolus time. For the other challenge during the same treatment period, use the bolus calculator but change the bolus time to 45 minutes late.

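### The late-versus-normal bolus contrast is measured from 45 minutes before the two conditions can differ, and at ages 2-5 it stops 2 h 15 min after the bolus

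*Combined protocol and SAP*

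**What the plan says.** Section 5.1.1 fixes the origin of each challenge: "Time zero (start of the challenge) is at the first bite of food for the study meal". Step 6 of that section applies to both challenges in a treatment period: "Bolus for the meal 45 minutes after starting to eat, entering the full carbohydrate amount and using the" calculator's recommended dose. The two conditions separate only there. In one challenge participants "use the bolus calculator but do not change the bolus time"; in the other they "use the bolus calculator but change the bolus time to 45 minutes late".

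Section 8.6.4 limits the challenge data: "restricted to data during the meal challenge window (start of meal through 5 hours from meal imitation [3 hours for age 2-5"]. Section 8.6.4.2 also counts time to intervention from the start of the meal.

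Secondary endpoints 7 to 9 in section 8.4 compare late bolus feature use with a normal bolus. The comparisons spelled out in 8.6.4.1 and 8.6.4.2 are between treatment periods, that is, between glucose targets.

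Under the synopsis, CGM data from the challenge periods do not enter the overall CGM metrics. Data recorded after the window closes do enter them.

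**The concern.** Safety after late bolus meal challenges, preschoolers included, is among the study objectives. Section 1.3.1.3 names the hazard: requiring "boluses to be delivered late, could increase the risk of hypoglycemia". The final-visit instructions in section 3.4.1 also recognise that insulin on board can stay active for a few hours.

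Two features of the window work against the contrast that endpoint 7 is meant to make. It includes a stretch in which the two conditions are procedurally the same, and this stretch is a larger share of the window in the youngest cohort. At ages 2-5 it also ends soon after the bolus, so a later low cannot be attributed to one bolus condition or the other. The documents give no reason for the shorter preschool window.

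At stake is how well the study can describe the late bolus feature in the cohort with the fewest participants: at least 12 completers with four challenges each, or 12 × 4 = 48 challenges, 24 per bolus condition.

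**Working it through.** The plan states no figure of its own to reproduce here. The check is interval arithmetic.

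**Inputs**
- Window W, from first bite: 300 min at age 6+, 180 min at ages 2-5 (section 8.6.4).
- Bolus time, both conditions: 45 min (section 5.1.1, step 6).
- Duration of insulin action: not given, so it is varied below as an assumption.

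**Share of the window before the bolus = 45/W**
- Age 6+: 45/300 = 15%.
- Ages 2-5: 45/180 = 25%.

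**Time observed after the bolus = W − 45**
- Age 6+: 300 − 45 = 255 min (4 h 15 min).
- Ages 2-5: 180 − 45 = 135 min (2 h 15 min).

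**Dilution of a percent-time difference.** If the conditions do not differ before the bolus and CGM coverage is even across the window, the whole-window difference is the post-bolus difference × (W − 45)/W.
- Age 6+: 255/300 = 0.85.
- Ages 2-5: 135/180 = 0.75.

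As an illustration, take 15 min below 70 mg/dL, all of it after the bolus. At age 6+ this is 15/300 = 5.0% of the planned window and 15/255 = 5.9% of the post-bolus part. At ages 2-5 the figures are 15/180 = 8.3% and 15/135 = 11.1%.

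**Share of an assumed at-risk period of h hours after the bolus that is observed = min(1, post-bolus time/h)**

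| Assumed h | Ages 2-5 | Age 6+ |
|---|---|---|
| 2 h | 100% | 100% |
| 3 h | 135/180 = 75% | 100% |
| 4 h | 135/240 = 56% | 100% |
| 5 h | 135/300 = 45% | 255/300 = 85% |

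At ages 2-5 there is a gap for any assumption above 2 h 15 min.

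**Where the preschool hours from 3 to 5 go.** They return to the overall CGM metrics, whereas the same hours are removed at age 6+. The amount is at most 2 challenges × 2 h = 4 h per two-week period. The period has 336 h, less 2 × 3 h of challenge windows, so 330 h, and 4/330 = 1.2%. Both targets carry two challenges, so the comparison of targets is balanced. The run-in, which section 8.2 makes the comparator, has no challenges.

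**The case against.** Much of the case for leaving the plan alone is sound.

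- **The cut-off follows the conduct rules.** At ages 2-5 the limits on extra boluses, carbohydrate, exercise and sleep activity all end at 3 h, so later data are less controlled. This stands, and it is why the later hours belong in a supplementary segment. It cannot be assumed that the loss of control is equal under both conditions, because the order of the two challenges within a period is not stated to be randomised.
- **The shared 45 minutes do not bias the contrast.** They dilute it and add noise. For time to intervention, moving the origin by the same 45 min leaves log-rank and Cox results unchanged, apart from interventions before the bolus. Those should be few: participants are eating, and a trigger of more than an hour above 300 mg/dL cannot be met within 45 min from the permitted starting values.
- **For the target comparison the first 45 minutes are informative**, since the assigned target is active from the first bite. The planned window should therefore not be replaced.
- **Safety is not lost.** Reportable adverse events at any time are tabulated and listed. Real-time CGM alerts cover all 2-5 year olds throughout Control-IQ 2.0 use, and contact with staff follows each challenge within a day.
- **Interventions after 3 h may not be recorded.** Non-severe hypoglycemia is generally not a reportable event, and the logbook page covers the challenge. Nothing says that later carbohydrate treatments are captured.

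The study is exploratory, has no formal hypotheses, and its sample size has no statistical basis. That limits the weight of the point but does not restore the missing link between later preschool lows and bolus condition.

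**Conclusion.** The point holds in a limited form. For the late-versus-normal contrast, 15% of the window at age 6+ and 25% at ages 2-5 comes before any possible feature effect, so a post-bolus percent-time difference is reported at 0.85 or 0.75 of its size. This assumes a bolus at the nominal 45 min, even CGM coverage, and no difference between conditions before the bolus. At ages 2-5, lows more than 2 h 15 min after the bolus are tied to bolus condition in no challenge endpoint.

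A reader might infer that late-bolus lows in preschoolers are missed altogether. They are not: those in the first 135 min after the bolus count in every challenge endpoint, and later ones reach the overall CGM metrics and, if reportable, the adverse-event tables.

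A reader might also take four hours as the protocol's duration of bolus action and conclude that just over half of it is seen. The four-hour rule in section 3.1.3 concerns insulin given outside the pump: "If correction insulin is administered via insulin syringe, turn Control-IQ off for four hours and until" glucose has fallen below a stated level. It is not a duration of action. The observed share is therefore a range, 45% to 100% for assumptions of 5 h down to 2 h.

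**What to change.** In section 8.6.4, keep the planned window and keep the target comparison from meal start. For the late-versus-normal contrast, add:

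1. CGM metrics from the recorded bolus time to the end of the window, with interventions before the bolus shown separately.
2. For ages 2-5, CGM metrics and reported adverse events at 3-5 h after meal start, by bolus condition, as a separate supplementary segment. Include interventions in that segment only if they were recorded.

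As a sensitivity analysis, also drop the preschool hours 3-5 from the overall CGM metrics. This removes at most about 4 h per two-week period and mainly affects comparisons with the run-in.

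The cost is some SAP wording and a few derived windows on CGM data that are already collected. The drawback is that the 3-5 h segment is less controlled, because the challenge restrictions have ended and sleep activity resumes, so it should be read descriptively. No change to conduct, supervision or dosing is proposed.
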